## **Johns Hopkins Medicine - eIRB Protocol (eForm A)**

- Use the section headings to write the eForm A, inserting the appropriate material in each. If a section is not applicable, leave heading in and insert N/A.
- When submitting eForm A (new or revised), enter the date submitted to the field at the top of eForm A.

\*\*\*\*\*

### **1. Abstract**

This research proposal aims to explore the efficacy of recombinant human erythropoietin versus placebo in promoting the recovery of erectile function in patients undergoing bilateral nerve-sparing radical prostatectomy for clinically localized prostate cancer. The proposal represents a translational objective deriving from findings from the [name] urological laboratory that have defined neuroprotective and neurotrophic roles of erythropoietin involving the penile autonomic innervation following cavernous nerve injury. We have completed preclinical studies in a rat model of cavernous nerve injury that mimics the cavernous nerve trauma of radical prostatectomy in which we showed erythropoietin potently promotes the recovery of erectile function. We have also shown that the erythropoietin receptor is expressed in rat major pelvic ganglia and cavernous nerves and preliminarily confirmed similar findings in innervation of the human penis. This work suggests the potential benefit of using erythropoietin to promote erectile function recovery rates in men undergoing radical prostatectomy and other pelvic surgeries. A retrospective comparison of 36 patients at Johns Hopkins suggested a benefit in erectile function for patients receiving erythropoietin. Our hypothesis is that erythropoietin offers neuroprotection for the penile autonomic innervation in men undergoing nerve-sparing radical prostatectomy, and we plan to conduct a randomized controlled trial to demonstrate enhanced recovery of erectile function postoperatively.

**Specific Aim: To evaluate the effect of short-term perioperative recombinant human erythropoietin administration on erectile function recovery in men undergoing bilateral nerve-sparing radical prostatectomy.** The research proposal will test the hypothesis that erythropoietin exerts neuromodulatory effects that will result in a reduced time interval of erectile dysfunction and an improved rate of erection recovery after this surgery. The aim relates to the knowledge that nerve trauma occurs even during cavernous nerve-sparing radical prostatectomy and this neuropathic event affecting the penis largely accounts for the temporary or permanent erectile dysfunction observed in many men undergoing the surgery. The investigation will apply a single center, randomized, double-blind, placebo-controlled 12 month study design and employ validated instruments to assess erectile function, urinary continence, and health related quality of life status.

### **2. Study Procedures**

The study design will be a single center, randomized, double-blind, placebo-controlled, 2-arm study, comparing the effects of recombinant human erythropoietin vs. saline placebo on erectile function recovery in men after bilateral nerve-sparing radical prostatectomy. The dosing regimen: a three (3) day

Date: March 16, 2017

Principal Investigator: [name].

Application Number: IRB00048594

intensive treatment of 300 units/kg subcutaneously and then 33,000 units intravenously was used in a previously reported clinical trial of erythropoietin for acute stroke. Similarly, the dosing regimen for this clinical trial will be ~300 units/kg subcutaneously for a 3-day treatment plan – the exact dose will be 20,000 units given as a subcutaneous treatment on the day prior to surgery and 20,000 units given subcutaneously on the day of and day after surgery.

The sample size will be 25 patients randomized to each study arm (50 patients total). Study procedures will involve screening and informed consent after initial consultation, baseline evaluation including medical clearance and completion of validated questionnaires, randomization, therapy (preoperative day dosing, dosing 0-2 hours prior to surgery, postoperative day 1 dosing), follow-up with blood draw for hematocrit and hemoglobin levels at 2 weeks post-op and then follow-up (completion of efficacy questionnaires at 3, 6, 9 and 12 months postoperatively). Assessment tools will consist of the following questionnaires which will be administered online using a REDCap site hosted by the Data Informatics Services Core within the Johns Hopkins Biostatistics Center or via mail per patient preference: IIEF questionnaire, the Quality of Erection Questionnaire (SEQ), and the version of the Expanded Prostate Cancer Index Composite (EPIC) that combines the Short Form Health Survey (SF-12) and AUA Symptom Index (AUA-SI). Standard practice associated with surgery, blood transfusion and postoperative laboratory testing will be performed. Patients will be prescribed a phosphodiesterase type 5 inhibitor (sildenafil, tadalafil or vardenafil) at 1 month following surgery to be used as conventional “on-demand” therapy. Adverse event monitoring will be performed. PSA monitoring is recommended at 3 and 12 months with the definition for biochemical recurrence set a PSA of 0.2ng/mL (rising from an undetectable level after surgery).

#### EPO Erection Recovery following RRP Protocol

	Consult	Baseline Eval	Pre-Op Day	Surgical Day	Post-Op Day 1	Post-Op Day 2	Two Weeks Post-Op	One Month Post-Op	Three Months Post-Op	Six Months Post-Op	Nine Months Post-Op	Twelve Months Post-Op
Informed Consent	✓											
Medical Clearance		✓										
IIEF 		✓						✓	✓	✓	✓	✓
SEQ		✓						✓	✓	✓	✓	✓
EPIC, SF12, AUASI 		✓						✓	✓	✓	✓	✓
Randomization	✓											
Blood work (HCT)			✓	✓	✓	✓	✓					
EPO Administration			✓	✓	✓							
RX – (Phosphodiesterase type 5 inhibitor)								✓				
AE monitoring 			✓	✓	✓	✓		✓	✓	✓	✓	✓
PSA monitoring									✓			✓

Questionnaires will be administered online using REDCap or via mail per patient preference

Postoperative AE monitoring will be performed by an RN or MD via telephone

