## 6. Risks

Completion of the questionnaires and administration of EPO are the only 2 procedures from this protocol that are outside of the realm of standard of care for the radical prostatectomy patient. All of the questionnaires will be completed by the participants pre-operatively allowing them time to assess if this activity is something they are willing to complete 4 times post-operatively. If the questionnaires cause any type of discomfort or uneasiness at that time or any time during the study, the participant can decide to end their involvement with the protocol.

Date: March 16, 2017

Principal Investigator: [name].

Application Number: IRB00048594

Possible adverse effects of EPO include pain, redness or swelling at the injection site, headache, joint or muscle pain, nausea, vomiting, indigestion, stomach pain, diarrhea, constipation, runny nose, sneezing, difficulty falling or staying asleep, excessive sweating, or rash.

Serious adverse effects associated with EPO (extremely rare) include anaphylaxis, cerebrovascular accident, deep venous thrombosis, hypertension, acute left ventricular failure, myocardial infarction, pulmonary embolism, seizure, thrombotic disorder, hemoptysis, chronic cough, production of antibodies causing severe anemia, transient ischemic attack, aphasia, confusion and death.

The occurrence of any serious adverse effects will end the patient's participation in the study and halt enrollment in the study to determine the safety of continuing the study. Each and every possible adverse effect of EPO will be investigated and treated individually to minimize the participant's discomfort. The safety of having the individual complete the study will also be assessed on an individual basis. At any time the participant can decide to terminate his participation in the study and no penalty or loss of benefits to which they are entitled.

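### No adverse-event check is scheduled between post-operative day 2 and one month (26 to 29 days), although the men are already due a blood draw at two weeks

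*Combined protocol and SAP*

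**What the plan says.** The schedule table in Section 2 (headed EPO Erection Recovery following RRP Protocol) ticks AE monitoring on the pre-operative day, the surgical day, post-operative days 1 and 2, and then at 1, 3, 6, 9 and 12 months. The two-week cell in that row is empty. The two-week column holds a single tick, for blood work.

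The table footnote sets the method: "Postoperative AE monitoring will be performed by an RN or MD via telephone". It gives no dates.

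The text of Section 2 describes the two-week contact only as "follow-up with blood draw for hematocrit and hemoglobin levels at 2 weeks post-op". On safety it says "Adverse event monitoring will be performed", without a time point. Dosing is 20,000 units on the day before surgery, then "20,000 units given subcutaneously on the day of and day after surgery", so the last dose is on post-operative day 1.

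Section 6 lists serious effects that include "anaphylaxis, cerebrovascular accident, deep venous thrombosis, hypertension, acute left ventricular failure, myocardial infarction, pulmonary embolism". It says that any serious adverse effect will end that patient's participation and "halt enrollment in the study to determine the safety of continuing the study".

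**The concern.** The gap in scheduled AE checks begins one day after the last dose and covers nearly all of the first month after surgery. Section 6 acts on a single serious event, so the review it triggers can start only once that event is known. If a man has a thrombotic event in this window and it does not reach the study team through him or his clinicians, the plan does not ask him about it until the one-month call. Enrolment could continue in the meantime.

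Milder effects listed in Section 6, such as headache, rash, nausea or poor sleep, would rest on about four weeks' recall.

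The delay is possible rather than certain. Both arms follow the same schedule, so the issue is timely safety oversight and not a biased comparison.

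**Working it through.** The plan gives no figure of its own for this interval, so there is none to reproduce. The check has four steps.

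**1. Is the blank cell real?** The table header has 13 cells (a label and 12 visits). The AE, blood-work, IIEF, EPO and PSA rows, compared cell by cell, also have 13 each. The AE ticks after the blank fall in the same 1, 3, 6, 9 and 12 month columns as the questionnaire ticks. No column has shifted, and the empty cell is not an extraction fault.

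| Row | Day 2 | Two weeks | One month |
|---|---|---|---|
| Blood work | ticked | ticked | – |
| AE monitoring | ticked | – | ticked |
| IIEF | – | – | ticked |

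Neither the text of Section 2, the footnote nor Section 6 adds an AE date between day 2 and one month.

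**2. Length of the gap.** Inputs: last early AE check on day 2; next check at one month. The documents do not define a month or give a visit window, so 28 to 31 days is an assumption.

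- Between checks: 28 − 2 = 26 to 31 − 2 = 29 days.
- From last dose (day 1) to the next check after day 2: 28 − 1 = 27 to 31 − 1 = 30 days.
- With a check at day 14: 14 − 2 = 12 days, then 28 − 14 = 14 to 31 − 14 = 17 days.

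**3. Mean wait until a scheduled check.** This applies only to an event that becomes known solely at a scheduled check, with timing assumed even over the gap. For one gap of length L the mean wait is L/2. For a gap split into a and b it is (a² + b²) / [2(a + b)].

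| | Month = 28 days | Month = 31 days |
|---|---|---|
| Now | 26/2 = 13 days | 29/2 = 14.5 days |
| With day-14 check | (12² + 14²)/(2 × 26) = 340/52 = 6.5 days | (12² + 17²)/(2 × 29) = 433/58 = 7.5 days |
| Saving | 6.5 days | 7.0 days |

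The longest possible wait falls from 26–29 days to 14–17 days.

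The documents do not say what share of events would be learned of only in this way. If that share is s, the mean saving over all events in the gap is s × 6.5 to s × 7.0 days. It is zero at s = 0 and reaches 6.5–7.0 days only at s = 1.

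**4. Workload.** With 50 men all completing every contact: 9 × 50 = 450 scheduled AE checks now, 10 × 50 = 500 with the added tick. The increase is 50/450 = 11%.

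**The case against.** The reading of the table and the arithmetic are not in dispute. The case on the other side is about weight.

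- **The halt rule does not wait for a scheduled call.** Section 6 responds to the occurrence of a serious effect, however it becomes known, and the statement in Section 2 that AEs will be monitored has no date limits. Stroke, myocardial infarction, pulmonary embolism and deep venous thrombosis would often come to light through clinical care. This stands, and it limits the benefit to the events missed by those routes.
- **The men are seen in the gap.** The two-week draw is a contact, and ordinary post-surgical care continues. This also stands in part: staff may well ask how the patient is. The protocol does not require the question or its recording, so the draw is not an AE check. Nor does the draw show that the sponsor saw a safety need at two weeks, since change in hemoglobin is a secondary outcome in Section 5.
- **Later gaps are longer.** Checks are two months apart between months 1 and 3 and three months apart after that, and the documents set no interval that the plan breaches. True, but the gap at issue is the one closest to dosing and surgery.
- **The mean-wait figures look firmer than they are.** They cover only events found solely at a scheduled check, under even timing. Across all events they are an upper bound, and should be read as one.
- **No analysis is affected.** AEs are not among the outcomes in Section 5. This is correct; the point concerns safety oversight and description only.

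The blank may be clerical or deliberate. The documents do not settle which, and the remedy is the same.

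**Conclusion.** The concern holds as a minor improvement. The schedule leaves 26 to 29 days without a solicited AE check, starting the day after dosing ends, and the one blank AE cell from the pre-operative day onward sits at a contact that already takes place.

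The gap's length rests on a month of 28 to 31 days. The roughly halved mean wait rests further on even event timing and on events known only at a scheduled check; averaged over all events, the saving is smaller to an unknown degree. Section 6 describes serious effects as very rare, so the expected gain is small. The number of further men who might be dosed during a delay cannot be stated, because the documents give no accrual rate. Confidence that the point is worth acting on is moderate; there is little doubt about what the table shows.

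**What to change.** Tick AE monitoring in the two-week column, done by an RN or MD by telephone around the time of the blood draw and recorded in the same way as the other AE checks. Treatment, endpoints and the Section 6 halt rule stay as they are.

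The cost is one short call or AE form per man, about 50 in all. The drawback is that staff time, spent for a small expected return.

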**An IND# application has been filed and approved by the FDA for this protocol, IND 100,709.**

Date: March 16, 2017

Principal Investigator: [name].

Application Number: IRB00048594

### 3. Inclusion/Exclusion Criteria

#### Inclusion Criteria:

1. Male sex 40 to 65 years of age with localized prostate cancer (clinical stage  $\leq$  T2a, Gleason grade  $\leq$  3+4=7 (Gleason 8 or 4+3=7 will be excluded), PSA  $<$  10 ng/mL)
2. Scheduled to undergo curative radical prostatectomy applying bilateral nerve-sparing procedure
3. Intact pre-surgical erectile function (International Index of Erectile Function [IIEF]-5 / Sexual Health Inventory for Men (SHIM) score  $\geq$  22)
4. Willingness to attempt intercourse at least 5 times per month following surgery.
5. Has a sexual partner of at least 6 months with current sexual activity (within the past 4 weeks)
6. Pre-surgical hematocrit  $\leq$  48.

#### Exclusion criteria:

1. Known penile deformity or a history of Peyronie's disease
2. Pre or post operative androgen therapy
3. Pre or post operative radiation therapy
4. Taking anticoagulation therapy
5. History of sickle cell anemia
6. History of high or low blood pressure that is not controlled
7. Taking nitrates medications
8. History of heart problems such as angina, heart failure, irregular heartbeats, or myocardial infarction
9. History of drug or alcohol abuse
10. Current smoker has a 20 pack/year history of cigarette smoking
11. History of acute or chronic depression
12. History of liver problems or kidney problems
13. History of retinitis pigmentosa or severe vision loss, including a condition called NAION
14. History of spinal trauma or surgery to the brain or spinal cord
15. Other contraindications to the use of PDE 5 inhibitors
16. Patient is currently participating in another clinical investigation that would serve as a contraindication to administering erythropoietin.

### 4. Drugs/ Substances/ Devices

Erythropoietin (EPO) is a cytokine-hormone that stimulates erythropoiesis under hypoxic conditions. Recently, EPO protein and its receptor have been found to be abundantly expressed within the central and peripheral nervous systems. Exogenous administration of EPO in animal models focusing on brain, spinal cord, and sciatic nerve injury has resulted in attenuated neuronal damage and hastened recovery. In humans, a recent clinical trial confirmed the therapeutic efficacy and safety of recombinant human EPO (rhEPO) administration in patients suffering from acute ischemic stroke. The recently established role of EPO as a neurotrophic factor makes it an attractive drug to evaluate in the context of neurogenic erectile dysfunction.

Date: March 16, 2017

[figure not shown]
Principal Investigator: [name].

Application Number: IRB00048594

This body of work stimulated a study in our laboratory to investigate the effects of EPO administration on a validated cavernous nerve injury rat model of erectile dysfunction. Male Sprague-Dawley rats underwent unilateral CN transection with excision of a 5mm segment of the contralateral CN, as described previously. A group of animals received daily EPO treatment, and a group received EPO pretreatment (24 hours and 1 hour prior to injury). The appropriate control groups consisting of saline treatment and pretreatment as well as a sham group (nerve dissection but no injury) were also included in this study. On day 14 following the injury, the rats underwent electrical stimulation of the transected nerve with simultaneous intracavernous pressure (ICP) and systemic arterial pressure monitoring. This model of nerve injury endures a reproducibly exact peripheral nerve injury while preserving the alignment of the CN permitting nerve recovery and simultaneously serving to connect the measured erectile response exclusively to the recovery of the injured nerve supply.

Exogenous treatment with daily doses of rhEPO starting 24 hours prior to CN injury preserved erectile function to a greater extent than saline treatment at 14 days following injury (Figure 1). Erection recovery, calculated as stimulated ICP area above the baseline pressure indexed to systemic pressure, was significantly greater for rats treated with daily rhEPO than for controls treated with saline ( $20.3 \pm 2.9$  versus  $8.6 \pm 3.2$ ,  $p < 0.05$ ). Daily treatment for 14 days resulted in a significant increase in the hematocrit values of treated animals (51.4 vs. 65.8,  $p < 0.01$ ). Because of the clinical ramifications of this effect and in light of data supporting the efficacy of pretreatment regimens in the context of nerve injury, a group of rats underwent a pretreatment protocol. Pretreatment with rhEPO (24 hours and 1 hour prior to CN injury) resulted in erection recovery comparable to that of daily treatment ( $20.3 \pm 4.0$  versus  $20.3 \pm 2.9$ ,  $p = 0.99$ ) without significant changes in hematocrit values (48.9 vs. 48.2,  $p = 0.56$ ). Treated animals achieved recovery of erections to approximately 60% of those achieved by sham treated rats. Treatment of sham animals with daily rhEPO had no effect on erectile responses after 14 days.

**Figure 1.**

- Representative tracing showing ICP responses to CN electrical stimulation. In the rhEPO treated animal, stimulation of the transected CN produced substantial erection recovery in contrast to the saline treated animal.
- Mean ICP area normalized to the systemic pressure  $\pm$  SEM when stimulating transected right CN after treatment with saline, rhEPO daily, and rhEPO pretreatment versus sham treatment. (I+Saline=CN injury treated with saline, I+EPO=CN injury treated with daily rhEPO, I+PreEPO=CN injury pretreated with rhEPO, Sham=Sham animals treated with saline, Sham+EPO=Sham animals treated with daily rhEPO). a,  $p < 0.02$  vs. I+Saline; b,  $p < 0.01$  vs. Sham; c,  $p < 0.04$  vs. I+Saline; d,  $p < 0.02$  vs. Sham; e,  $p = 0.94$  vs. Sham+EPO; f,  $p < 0.001$  vs. I+Saline.

To identify the presence of EPO receptors in major pelvic ganglia (MPG) and penile tissues, we performed immunohistochemistry on rat tissue sections. EPO receptor was localized to the neuronal

Date: March 16, 2017

Principal Investigator: [name].

Application Number: IRB00048594

bodies within the MPG. RT-PCR confirmed the presence of EPO receptor mRNA in MPG tissue. EPO receptor mRNA levels were unchanged one day after injury and saline treatment but were increased by approximately 7 fold with injury and EPO treatment at the same time point. EPO receptor immunoreactivity in the penis was observed in the penile dorsal nerves, sinusoidal endothelium of the corpus cavernosum, and endothelial cells lining the dorsal vein and arteries. In addition, preliminary immunolocalization studies of human tissues reveal positive staining for the EPO receptor in the axons of widely excised neurovascular bundles. All slides processed without primary antibody or with blocking peptide showed no staining.

Electron microscopy was used to examine the CN distal to the site of injury and to assess axonal regeneration. The number of axons per Remak bundle in addition to the morphology of these axons was used to determine regeneration within the CN. Sham (intact) animals had a mean of  $4.9 \pm 0.2$  axons per Remak bundle while injured animals treated with saline had a mean of  $1.0 \pm 0.1$  ( $p < 0.001$ ). Daily rhEPO treatment resulted in a greater recovery of axons per Remak bundle when compared to saline treated animals ( $2.7 \pm 0.2$  versus  $1.0 \pm 0.1$ ,  $p < 0.001$ ). Sprouting of unmyelinated fibers typically passes through a phase in which Remak bundles contain very small unmyelinated axons or axons in polyaxonal pockets. Such profiles were evident in all rhEPO treated animals, suggesting neuronal regeneration.

Thus, we have shown that EPO promotes the recovery of erectile function in a rat model of nerve injury and that the EPO receptor is expressed in penile nerves and endothelium of penile blood vessels.

## 5. Study Statistics

The primary outcome variable is the patient's score on the IIEF questionnaire (erectile function domain) at 3, 6, 9, and 12 months post-surgery.

The secondary outcome variables will be the patient's scores on the QEQ, combined EPIC/SF-12/AUASI questionnaires, other domains of the IIEF questionnaire, and change in hemoglobin.

For statistical analysis based on ANOVA, the sample size is powered for a power of 80% with one-sided alpha of 0.05 showing a sample size of 23 patients in each arm is necessary to detect an expected difference of 5 points in IIEF scores (i.e. 20 vs. 15) at 6 months post-surgery. Therefore, the study is planned to enroll 25 patients in each arm.

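### Does naming ANOVA alongside a one-sided alpha of 0.05 undermine the trial's stated 80% power?

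*Combined protocol and SAP*

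**What the plan says.** Section 5 (Study Statistics) is the only statistical text. It names the method and the error rate together: "For statistical analysis based on ANOVA, the sample size is powered for a power of 80% with one-sided alpha of 0.05". It continues that "a sample size of 23 patients in each arm is necessary to detect an expected difference of 5 points in IIEF scores", taken as 20 versus 15 at 6 months, and plans 25 per arm. It gives no standard deviation, does not describe the form of the ANOVA, and states no significance level apart from the one in the sizing sentence. The primary outcome in the same section is the erectile function domain score at 3, 6, 9 and 12 months.

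On direction, Section 1 (Abstract) says "we plan to conduct a randomized controlled trial to demonstrate enhanced recovery of erectile function postoperatively". The Specific Aim in that section likewise hypothesises a shorter period of dysfunction and a better recovery rate. Section 2 (Study Procedures) describes a two-arm design "comparing the effects of recombinant human erythropoietin vs. saline placebo on erectile function recovery".

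**The concern.** A two-group F test rejects for a large difference in either direction, and its p-value is by habit read against 0.05. The sample size rests on "a power of 80% with one-sided alpha of 0.05". If the analysis used F at 0.05, the trial would be sized on a more lenient criterion than the one applied, and real power would fall below the stated 80%.

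The decision rule is also at stake. A result favouring erythropoietin with an F-test p-value between 0.05 and 0.10 succeeds under one-sided 0.05 and fails under F at 0.05. If the rule were open, it could be chosen after the data were seen.

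**Working it through.** **Inputs.** From Section 5: difference 5 points, one-sided alpha 0.05, power 80%, 23 per arm required, 25 planned. The standard deviation (SD) is not stated, so it is back-solved. The comparison is taken as two equal groups at 6 months, without baseline adjustment, with all patients evaluable.

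**Formulas.** With n per arm, df = 2n − 2 and noncentrality δ = 5 / (SD × √(2/n)).
- One-sided power = P(t′(df, δ) > t(0.95, df)), where t′ is noncentral t.
- F-test power = P(F′(1, df, δ²) > F(1 − α, 1, df)), where F′ is noncentral F.

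**Step 1: the plan's figure of 23.** One-sided power at 0.05 equals exactly 80% at n = 23 when SD = 6.714, and at n = 22 when SD = 6.561. So 23 is the smallest adequate n for SDs between about 6.56 and 6.71. A normal approximation gives 6.67 to 6.82. Because the SD is inferred from 23, this shows what 23 implies; it does not verify it independently.

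**Step 2: worked case at SD 6.7.**
- n = 23: δ = 5 / (6.7 × √(2/23)) = 2.53; one-sided power 80.1%.
- n = 25: δ = 5 / (6.7 × √(2/25)) = 5 / 1.895 = 2.64; one-sided power 83.0%.

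**Step 3: the alternatives over the implied SD range.**

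| Rule | 23 per arm | 25 per arm |
|---|---|---|
| One-sided contrast at 0.05 | 80.0–81.6% | 82.9–84.4% |
| F at 0.10 | 80.0–81.6% | 82.9–84.4% |
| F at 0.05 | 69.5–71.5% | 73.2–75.2% |

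The first two rows agree because, with two groups, F = t². F at 0.10 is the two-sided t test at 0.10, whose upper half is the one-sided test at 0.05. The declared alpha therefore carries over to a two-group ANOVA without loss.

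**Step 4: where the rules would disagree at 25 per arm.** With df 48 the critical t values are 1.677 (one-sided 0.05) and 2.011 (two-sided 0.05), so F lies between 1.677² = 2.81 and 2.011² = 4.04. At SD 6.7 the standard error is 1.895, and the band is an observed difference of 1.677 × 1.895 = 3.18 to 2.011 × 1.895 = 3.81 points. The chance of landing there in favour of erythropoietin is 9.6% if the true difference is 5, and 0.05 − 0.025 = 2.5% if it is zero.

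**The case for a change.** The strongest case for a change is that the one-sided alpha appears only in the sizing sentence. Someone running a standard ANOVA and reading its p-value against 0.05 would break no written instruction. A directional hypothesis is not the same as a one-sided test, and Section 2 speaks neutrally of comparing effects. In a 50-patient trial, a chance of about 1 in 10 of a disputed result at the planned effect is not trivial, and one sentence would settle it.

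Part of this stands: the mapping from alpha to test is not written out, the SD is missing, and the conditional 73% to 75% is correctly calculated. The rest is weaker. F at 0.05 is a convention brought in from outside; adopting it means setting aside the only alpha the plan declares. The neutral phrase in Section 2 describes the design and does not conflict with a one-sided test, while Section 1 points the same way as Section 5.

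The 73% to 75% also depends on the model. Normal-approximation variants widen it to about 72% to 76%. A group effect averaged over the four visits would have different power again. As an illustration, take SD 6.7 at each visit, a constant 5-point difference and an assumed equal correlation r between visits. The SD of a patient's mean is then 6.7 × √((1 + 3r)/4), or 5.30 at r = 0.5 and 6.44 at r = 0.9. With F at 0.05 and 25 per arm, power is about 90% and 77% respectively.

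**Conclusion.** The concern does not require a change. Taken as written, the sizing sentence is coherent: a two-arm comparison, one-sided at 0.05 in favour of erythropoietin, with at least 80% power at 23 per arm and 83% to 84% at 25. No figure in Section 5 is shown to be wrong. The shortfall to 73% to 75% appears only under a test level that the document does not contain.

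The remainder is a gap that an analyst following the plan fills by testing the group contrast one-sided at the declared level. Writing that down would restate the declared alpha, and substituting F at 0.05 would replace it with one the plan never chose. Either wording, if tied to 6 months to match the power calculation, would also narrow a primary outcome listed at four time points, which is a separate design decision.

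These conclusions rest on an SD inferred from the plan's own 23 per arm and on an unadjusted 6-month comparison with complete data. Within the two-group setting, the equivalence of one-sided 0.05 and F at 0.10 in the favourable direction does not depend on the SD.

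### No baseline adjustment is specified for the IIEF or the secondary questionnaire scores, although every questionnaire is collected before surgery; adding it is a small efficiency gain, not a validity correction

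*Combined protocol and SAP*

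**What the plan says.** Section 5 (Study Statistics) defines the outcome as a score: "The primary outcome variable is the patient's score on the IIEF questionnaire (erectile function domain") at 3, 6, 9 and 12 months. The secondary outcomes are further questionnaire scores and change in hemoglobin. The only method named is in the sizing sentence: "For statistical analysis based on ANOVA, the sample size is powered for a power of 80% with one-sided alpha of 0.05". It continues that "a sample size of 23 patients in each arm is necessary to detect an expected difference of 5 points in IIEF scores", with 20 versus 15 at 6 months as the example. Section 2 sets enrolment: "The sample size will be 25 patients randomized to each study arm (50 patients total").

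Section 5 mentions no covariate, no baseline term and, apart from hemoglobin, no change score.

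Baseline data are nevertheless collected. Section 2 includes "baseline evaluation including medical clearance and completion of validated questionnaires" before treatment, the schedule table ticks IIEF, SEQ and EPIC/SF12/AUASI at the baseline evaluation, and Section 6 (Risks) confirms that participants complete all the questionnaires before the operation. Section 3 limits entry to men with an IIEF-5/SHIM score of 22 or more.

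**The concern.** In a randomised comparison of 50 men, the pre-treatment value of the outcome is the natural covariate. Without it, outcome variance that baseline could explain stays in the error term, and part of any chance baseline difference between arms carries into the estimated effect. No stratification factor is named, so nothing else in the described design deals with such a difference.

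There is also a pre-specification issue. Because Section 5 is silent, the choice between an adjusted and an unadjusted result could be made after the data are seen. At stake are precision and clarity about the analysis. The point is the same whichever visit or repeated-measures model becomes primary.

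**Working it through.** **Inputs from the documents:** difference 5 points, one-sided alpha 0.05, power 80%, 23 per arm required and 25 per arm enrolled (Sections 2 and 5). **Assumptions:** the SD (back-solved below) and the correlation r between baseline and 6-month score (0 to 0.5). Neither is stated.

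**1. The plan's own figure.** With no SD given, 23 per arm cannot be reproduced directly, so I solved for the SD. Two-sample power is the probability that a noncentral t with 2n − 2 df and noncentrality 5 / (SD × √(2/n)) exceeds the one-sided 5% critical value. At SD 6.71, 23 per arm gives 80.0%. At SD 6.56, 22 per arm already gives 80.01%, so 23 is the smallest adequate size for an SD just above 6.56 up to 6.71. The normal formula would give 6.67–6.81 instead.

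**2. Unadjusted power at 25 per arm (48 df).** √(2/25) = 0.283.
- SD 6.71: SE = 6.71 × 0.283 = 1.90, noncentrality 5/1.90 = 2.63, power 83.0%.
- SD 6.56: SE = 6.56 × 0.283 = 1.86, noncentrality 5/1.86 = 2.69, power 84.4%.

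**3. Adjusted power at 25 per arm (47 df).** Two things change. The residual SD becomes SD × √(1 − r²). The variance of the treatment estimate is also inflated by an expected factor of about 1 + 1/46, or 2.2%, because the slope has to be estimated while baselines differ by chance. Example, r = 0.3 and SD 6.71: residual SD = 6.71 × √0.91 = 6.40; SE = 6.40 × 0.283 × √(1 + 1/46) = 1.83; noncentrality 5/1.83 = 2.73; power 85.3%.

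| r | Residual variance | Power by formula (SD 6.71 / 6.56) | Power by simulation (SD 6.71 / 6.56) |
|---|---|---|---|
| 0 | ×1.00 | 82.2% / 83.7% | – |
| 0.1 | ×0.99 | 82.6% / 84.0% | 82.7% / 83.9% |
| 0.3 | ×0.91 | 85.3% / 86.6% | 85.3% / 86.8% |
| 0.5 | ×0.75 | 90.7% / 91.8% | 90.7% / 91.8% |

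The formula and simulation agree to within 0.2 points. Break-even is where (1 − r²)(1 + 1/46) = 1, so r² = 1/47 and r ≈ 0.15. At r = 0 the loss is about 0.7 points (84.4 − 83.7).

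**4. Which r is plausible for the IIEF?** The entry floor narrows baseline. If u is the ratio of restricted to unrestricted baseline SD, the correlation becomes r × u / √(1 − r² + r²u²). An unrestricted r of 0.5 then falls to 0.15/√0.7725 = 0.17 at u = 0.3, and to 0.25/√0.8125 = 0.28 at u = 0.5. The values of u are assumptions, but they point to the lower rows of r.

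**5. Chance imbalance.** The baseline difference between arms has SE √(2/25) = 0.283 baseline SD, so the probability that it is at least 0.4 SD in either direction is P(|Z| > 0.4/0.283 = 1.41) = 0.157. Its effect on the unadjusted IIEF difference is r × 0.4 × SD. At SD 6.7 this is 0.27 points for r = 0.1, 0.80 for r = 0.3 and 1.34 for r = 0.5, against the 5-point target.

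**6. Secondary scores.** Section 3 sets no entry limit on EPIC urinary, AUA-SI or SF-12 scores, so their baselines can vary freely and r may be higher. The documents contain nothing from which to calculate that gain.

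**The case against.** The strongest reply is that the primary analysis may gain nothing. Every man enters with good erectile function, so baseline IIEF may barely predict the 6-month score. Below a correlation of about 0.15, adjustment costs slightly more than it returns, and the cost is more than the one degree of freedom because the slope must be estimated. This stands, and it limits the size of the point.

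Three stronger readings are tempting, and the documents support none of them.

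- **That the plan excludes baseline.** ANOVA appears once, as the basis of the sample size, and a score is how the outcome is defined. Section 5 never says that baseline will be left out. What can be said is that no adjustment is specified.
- **That the unadjusted comparison is biased, or that an imbalance enters it in full.** Randomisation keeps the unadjusted test valid, and its standard error already allows for chance imbalance. The imbalance enters only multiplied by r.
- **That substantial power is being lost on the primary outcome.** That would need a correlation near 0.5, which is hard to expect above a SHIM floor of 22.

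The secondary-score argument is also qualified. Hemoglobin is already handled as change, and the other IIEF domains and the erection-quality questionnaire come from men selected for intact function. The argument is clearest for EPIC urinary, AUA-SI and SF-12 scores.

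What survives is that the data are scheduled for every man, the likely loss is under one power point, and silence leaves the adjustment decision open.

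**Conclusion.** The point holds as an efficiency and pre-specification improvement. It is not an error of validity. For the primary outcome, expect a change between a loss of about 0.7 power points, if baseline is not prognostic, and a gain of roughly 2 points at a correlation of 0.3. A gain of 7 to 8 points would need a correlation of 0.5. For secondary scores without an entry floor the benefit is likely larger, but its size is unknown.

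All power figures rest on an SD of 6.56–6.71 back-solved from the plan's own 23 per arm, on assumed correlations, on approximately normal scores, and on all 25 men per arm being analysed. The unstated SD is a separate gap. These figures do not confirm that the trial has the power it claims.

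**What to change.** In Section 5, replace ANOVA with ANCOVA, or with a repeated-measures model carrying the same term: post-surgery IIEF erectile function score on arm and baseline IIEF erectile function score, both pre-specified. State that each secondary questionnaire score will be analysed with its own baseline as covariate, and that baseline means the questionnaire completed before the first dose.

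Keep the one-sided 0.05 and the 25 per arm as stated. The sizing need not be reduced in anticipation of a gain. Age need not be added: the documents give no association between age and outcome, and each extra covariate has its own cost.

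The cost is a sentence or two of text, one degree of freedom and about 2% in variance for each model. No new data or patients are needed.
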